Based upon an extensive body of research on the neural correlates of cognitive reappraisal [48-50], we expect reappraisal training focused upon down-regulating reactions to negative emotional pictures to influence the neural pattern that reflects processing of negative emotional pictures, the PINES signature. The PINES is a particularly appropriate target, because it has been shown to vary monotonically with subjective emotion ratings and has been shown to be specific to picture induced negative emotion [33]. Moreover, we found in our preparatory study (C.1.3.3) that reappraisal training was associated with a significant reduction in activation of this region. Hence our milestone for R61 success will be based upon change in the PINES network (see C.2.2). Although not specified as milestones, we will also examine

ROI's identified in the reappraisal literature: the amygdala, and the top-down control regions: the ventrolateral prefrontal cortex (VLPFC), the dorsolateral prefrontal cortex (DLPFC), the dorsomedial prefrontal cortex (DMPFC), the dorsal anterior cingulate cortex (dACC), and the posterior parietal cortex (PPC) [48]. In addition, we will examine behavioral reappraisal success. The effect of reappraisal training upon all of these targets will be monitored at baseline and at weeks 2, 4 and 6 by means of our fMRI reappraisal task (see **C.2.6**. below).

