- C.3.2. Choice of Regions of Interest for Imaging Analyses. We will assess negative reactivity by examining activation of the Picture Induced Negative Emotion Signature (PINES) network. We selected this network because its activation has been demonstrated to be specific to and monotonically proportional to subjective reactions to the negative picture stimuli we are employing. Moreover, it has been shown to outperform the three ROI's, the amygdala, insula and ACC, and seven whole brain networks, including the salience, default and somatomotor networks, commonly associated with negative affect [33]. Although PINES network activation is our primary neural outcome measure, we will also separately examine activity in each of the above specific ROI's and in the salience, default and somatosensory networks. Although not primary outcome measures, we will also examine the effect of training upon the top-down control regions implicated in cognitive reappraisal that have been highlighted in the metaanalysis by Buhle et. al. [48]: the dorsolateral prefrontal cortex (dIPFC), the ventrolateral PFC (vIPFC), the posterior dorsomedial PFC (dmPFC) and the posterior parietal cortex (PPC). C.3.3 Outcome Measures. R61: The primary outcome measure will be change in PINES network activity. Other outcome measures will be change in activity in the top-down control regions described above and in behavioral valence ratings of the image stimuli during reappraisal. R33: The primary outcome measure will be change in BPD symptomatology (total score in the Zanarini Rating Scale for Borderline Personality, self-report (ZAN-BPD, [57])). Secondary outcome measures will be the ZAN BPD sector scores, Affective Lability Scale total (ALS, [58], Perceived Stress Scale (PSS; [59]), Difficulty in Emotion Regulation Scale Scores (DERS; [41]), Beck Depression Scale score (BDI) and State-Trait Anxiety Scale Score (STAXI). C.3.4 Rationale for Eye Gaze and Pupilometry Measures. Eye gaze direction will be assessed in both R61 and R33 phases to determine whether changes in BOLD activity during regulate conditions are associated with diversion of gaze [60] away from emotionally salient portions of the pictures. Change in pupil diameter (regulate-look) will be recorded during each scan, as an index of cognitive effort [61].

C.4.0 Specific Design and Methods

C.4.1 Subject Inclusion and Exclusion Criteria for R61 and R 33 Phases

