C.5.1 R61 Phase. Analyses for Aims R61-2a and R61-2b are described in image analysis (C.6.4, below). Aim R61-2c: Data will be checked for normality and appropriate transformations will be applied to normalize them. Data analysis will primarily use linear mixed models, incorporating fixed effects for Training Group (CRD and ES), Session, and Trial Type (Look Neutral, Look Negative, and Regulate Negative), and their interactions, as well as a random effect consisting of an intercept for each participant. We will examine additional models that incorporate and estimate random-effects slope variance across participants on the time effect (i.e., Session). Outcome variables will be repeated measures in self-reported negative affect and reappraisal success (defined as the Look Negative minus Regulate Negative behavioral valence rating at each Session). Although we do not anticipate large differences in

baseline characteristics between the groups, given that the trial is randomized, we will include variables that are strongly unbalanced at baseline (p< 0.01) as covariates in our models.

C.5.2 R33 Phase. Aim R33-1: The primary outcome measure is the Zanarini total score (ZTS;[57]). We compare the change in ZTS from baseline to end of treatment (EOT) between groups by mixed effect models with group, time and their interaction as fixed effects. A similar analysis will be carried out for the additional outcome measures specified in C.3.3. (Table 1), using the Holm's procedure for correction for multiple comparisons. Aim R33-2: The analysis will be as for R61 Aims R61-2 a,b and c. Aim R33-3: The analysis is described in imaging analysis section C.6.3. Aim R33-4: As above, we will use linear mixed models to examine change in ZTS as the outcome variable. Bonferroni corrections will be applied for multiple clinical outcome measures. P-values throughout will be 0.05, two tailed. All analyses will be conducted according to the intent-to-treat principle for both the R61 and the R33 phase. As a sensitivity analysis we will also consider models that adjust for the number of sessions actually received. Missing data will be assumed as MAR. Under this assumption, a mixed model approach that uses all available information will yield reasonable estimates of the effect sizes.

C.6. Image Acquisition and Analysis

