C.6.1 Image Acquisition. Participants will all be scanned 4 times in the R61 Phase (0, 2, 4, 6 weeks) or 2 times in the R33 Phase (Baseline, End-of-Treatment [EOT]) using the same 3 Tesla Siemens Skyra MRI system equipped with a 16-channel head coil. For each scan session, 4 series of 550 T2*-weighted images will be acquired during the 4 runs of the emotion regulation task using a multi-band echo-planar imaging sequence sensitive to the blood oxygenation level-dependent (BOLD) signal (multi-band factor = 7; repetition time = 1200 ms; echo time = 35 ms; flip angle = 60° ; field of view = 228 mm²; matrix = 108×108 ; slice thickness = 2.1 mm; 70 slices). A high-resolution anatomical image will be acquired with a T1-weighted magnetization-prepared rapid gradient echo (MP-RAGE) sequence.

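### Reappraisal success (C.5.1): the primary mixed model assumes equally correlated sessions; if correlation fades or learning rates differ, the week-6 change contrast exceeds its nominal 5%

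*Combined protocol and SAP*

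**What the plan says.** C.5.1 gives the main analysis for Aim R61-2c as a linear mixed model with fixed effects for training group, Session and Trial Type and their interactions, plus "a random effect consisting of an intercept for each participant". It names no residual covariance structure, robust standard error or degrees-of-freedom method. The next sentence adds: "We will examine additional models that incorporate and estimate random-effects slope variance across participants on the time effect". Nothing says when those models would replace the first.

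One of the two outcomes is "reappraisal success (defined as the Look Negative minus Regulate Negative behavioral valence rating at each Session". This is a single difference score per participant per session, so Trial Type drops out of its model. C.2.1 says the R61 targets, this one included, "will be monitored at baseline and at weeks 2, 4 and 6". The test level comes from C.5.2: "P-values throughout will be 0.05, two tailed".

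On the status of the outcome, C.3.3 says for R61: "The primary outcome measure will be change in PINES network activity". C.2.1 lists behavioural reappraisal success among the measures examined outside the milestone.

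**The concern.** With one score per session, a participant intercept with independent residuals is the compound-symmetry model. Weeks 0 and 6 are taken to be as strongly correlated as weeks 0 and 2, and every session has the same variance. All change contrasts then share one pooled within-person residual. If correlation declines with the gap between sessions, that residual is too small for change to week 6 and too large for change to week 2.

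Equal correlation is doubtful on the plan's own reasoning. Fig. 1 describes reappraisal success as building up gradually with training, and C.5.1 itself anticipates that the time effect may vary between participants. The behavioural effect seen before was small (d = 0.15 for valence ratings, C.2.2), so a raised false-positive rate matters when a behavioural finding at week 6 is interpreted. At stake is the reported p-value for that secondary result, and the lack of a rule for choosing between two listed models that can give different p-values.

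**Working it through.** **Inputs.** 39 analysed per group (C.7), 49 recruited per group (C.4.2.1), 1:1 allocation (C.4.3.1), four equally spaced scans (C.6.1), two-sided 0.05 (C.5.2). Session correlations of reappraisal success are not in the documents and are assumed below.

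**The plan's own figure.** A two-sample t-test with 39 per group and d = 0.65 has power 0.809, and 39/0.80 = 48.75, which rounds up to 49. Both reproduce. That calculation is for PINES; the plan states no operating characteristic for the behavioural model.

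**Step 1: what the model assumes.** With intercept variance t2 and residual variance s2, every session has variance t2 + s2 and every pair has covariance t2. The variance of any change score is therefore 2 x s2, whatever the gap.

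**Step 2: what it estimates.** With complete data and separate means for each group and session, s2 comes from the pooled within-person residual on 3 x (78 - 2) = 228 degrees of freedom. With unit variances and lag correlations r1, r2, r3, the model's change variance is 2(1 - m), where m = (3 r1 + 2 r2 + r3)/6.

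**Step 3: actual error.** The true variance of change at lag k is 2(1 - rk). With R = (1 - rk)/(1 - m), the error is 2[1 - Phi(1.96/sqrt(R))].

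**Step 4: worked case.** First-order autoregressive, 0.5: m = (1.5 + 0.5 + 0.125)/6 = 0.354, so the model's variance is 1.292.
- Week 6: true variance 2(1 - 0.125) = 1.75, R = 1.355, error 9.2%.
- Week 2: true variance 1.00, R = 0.774, error 2.6%.

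For random slopes with intercept and residual variances of 0.5 each and slope variance v per session step, the true week-6 variance is 1 + 9v and the model's is 1 + 10v/3. At v = 0.05 these are 1.45 and 1.167, giving R = 1.243 and error 7.9%.

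**Step 5: range over assumed structures.**

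| Assumed truth | Week-2 change | Week-6 change |
|---|---|---|
| Equal correlations | 5.0% | 5.0% |
| Lags 0.6/0.55/0.5 | 4.1% | 6.8% |
| Lags 0.6/0.5/0.4 | 3.4% | 8.4% |
| AR(1) 0.5-0.8, 70% of variance session noise | 4.4-4.6% | 5.8-6.0% |
| AR(1) 0.5-0.8, 50% session noise | 4.0-4.1% | 6.6-6.9% |
| AR(1) 0.5-0.8, 30% session noise | 3.3-3.5% | 7.5-8.1% |
| Random slopes, v = 0.01 to 0.05 | 4.7-3.9% | 5.6-7.9% |
| Random slopes, v = 0.10 | 3.1% | 10.1% |
| AR(1) 0.5 | 2.6% | 9.2% |
| AR(1) 0.8 | 1.6% | 12.4% |
| AR(1) 0.9 | 1.4% | 13.4% |

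Simulation of 20,000 null trials per structure agrees with the formula: 9.3% and 12.5% at week 6 for AR(1) 0.5 and 0.8.

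**Step 6: other tests under AR(1) 0.5-0.8.** Week-4 change runs at about 7%. The omnibus Group x Session test runs at 5.5-6.7%. A plain week-6 group difference stays at about 5%, although with random slopes it can reach 5-10%. If Session is entered as a linear trend, the group-by-trend test runs at about 11-15%.

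**Step 7: after repair.** A week-6 change contrast using its own variance has simulated error of 4.8-5.3% in every structure. The random-slope model listed in C.5.1 gives about 4% under AR(1) 0.5 and 0.8, and 4.9% when random slopes are the truth (1,500 trials each).

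**The case against.** **The size is assumed.** No session correlation is documented. The score is a difference between condition ratings of 40 trials each (C.2.5), with a different image set at each scan (C.4.3.1). Session-specific noise is therefore plausible, and it pulls the structure toward equal correlation. This stands. A reader might infer that the week-6 test simply runs at 9-12%. The documents do not support that, because the band needs nearly pure autoregressive decay or strongly varying slopes.

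**The plan names no week-6 contrast for this outcome.** It names main effects and interactions, and the omnibus interaction is only mildly affected. This also stands. Change from baseline is nonetheless the natural reading of Group x Session with week 0 as reference, and it matches the imaging contrasts in C.6.3.

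**The remedy is already listed.** Random-slope models bring the error to about 4-5%. This is largely right, but they are additional, with no rule giving them the decision.

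**Silence on residual covariance does not exclude correlated residuals.** That is literally true. But the intercept is the only dependence stated for the main model, so independent residuals are the ordinary reading.

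**A stronger reading** would be that the model tilts the choice of dose toward 6 weeks. The documents do not support it. The milestone rests on PINES (C.2.1, C.6.4), C.2.2 chooses among doses by effect size, and PINES change is compared by two-sample tests that do not use this model. With complete balanced data, the intercept-only fit also leaves the group-by-session estimates unchanged.

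**Conclusion.** The concern holds in a limited form. As written, the inference model for reappraisal success protects its 5% level for change contrasts only if all session pairs are equally correlated with equal variances. Otherwise the week-6 change contrast is anti-conservative, by about 1 to 3 percentage points under mild departures and about 4 to 7 under pure AR(1) of 0.5-0.8, while week 2 is tested too strictly. These figures assume 39 per arm and complete data; the planned 20% loss was not simulated. The outcome is secondary, and neither R61 dose selection nor the decision to proceed to R33 is touched. The change is worth making because it is cheap and removes an unresolved choice between two models.

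**What to change.** In C.5.1, for reappraisal success:
- Make the model used for inference a repeated-measures mixed model with Session as four categories, Group, and Group x Session, and an unstructured within-participant covariance (REML, Kenward-Roger degrees of freedom).
- Name a fallback if it does not converge, such as heterogeneous Toeplitz or the random-slope model already listed.
- Name the group contrasts in change from baseline at weeks 2, 4 and 6.
- Keep the intercept-only model as a sensitivity analysis.

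The cost is a few sentences of text, eight more covariance parameters (10 instead of 2) and slightly fewer error degrees of freedom, which is minor with 78 to 98 participants. A smaller change, declaring the listed random-slope model decisive and naming the contrasts, would close most of the gap.

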C.4.1.2. Exclusion Criteria. Subjects will not meet criteria for Schizotypal Personality Disorder (SPD). SPD is excluded to avoid a possible confound from the restricted affect that characterizes SPD. BPD subjects will not meet DSM-5 criteria for past or present bipolar I disorder, schizophrenia, schizoaffective disorder, substance dependence, organic mental syndromes, head trauma, CNS neurological disease, or seizure disorder. Subjects currently meeting DSM-5 criteria for PTSD will be excluded, unless they are in remission or not currently experiencing symptoms. Subjects currently meeting criteria for major depressive disorder will also be excluded (except as described above). However, since depression is commonly associated with BPD (Koenigsberg et al., 1999), too stringent a depression exclusion criteria would yield a clinically atypical BPD sample. For this reason, BPD patients with Axis I depressive disorders other than major depression and those with a past history of major depression, will not be excluded. Suicidal subjects will not be excluded, unless referral to a higher level of care is deemed clinically necessary by the evaluating clinician. Subjects must not have met criteria for a substance use disorder for 6 months prior to entry into the study. All subjects must be free of significant medical illness. They may not have a pacemaker, surgical clips, any metallic implants, or shrapnel fragments that would contraindicate MRI scanning. Pregnant women will be excluded.

C.4.2. Sample Size, Recruitment and Assessment

C.4.2.1 Sample Size. R61 Phase: (see Power Analysis C.4.5.1). 49 BPD subjects will be recruited each for the training and control groups to acquire 39 subjects in each group allowing for a 20% loss for drop out and fMRI movement artifact. R33 Phase: 65 BPD subjects will be recruited each for the training and control groups to obtain 51 subjects per group, allowing for 20% loss.

C.4.2.2 Recruitment:
Subjects will be recruited
by newspaper, radio,
and social media
advertisements and by
referral from the
psychiatry outpatient
department at Mount
Sinai Medical Center, the
Center for the Intensive
Treatment of Personality
Disorders at Mount Sinai
West, and the Bronx VA
Medical Center. We are
confident that we can
meet recruitment goals
for both R61 and R33 as
our Mood and
Personality Disorders
Research Program at
Mount Sinai, which has
been engaged in
neurobiological research
studies of BPD for over

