C.6.4 Second-Level Analysis of Group Differences in Treatment Effects. Randomeffects GLM will use two-sample t-tests to compare the neural effects of reappraisal-bydistancing (CRD) and control training. The 3 contrast maps (weeks 2, 4, 6) for each participant in the R61 phase and the EOT versus baseline contrast map for each participant in the R33 phase will be entered as dependent variables in separate GLM in which gender, age, education level, and pre-treatment ALS score will serve as covariates. The speculative purpose of the R61/R33 mechanism justifies setting the alpha level at a relatively liberal value of p<0.05 and a cluster threshold of 50 contiguous voxels. The hypothesized effects of treatment would be supported by findings of significant reductions in PINES activation for emotion regulation in the CRD training compared to the CD control training condition at either weeks 2, 4, or 6 or at EOT. The decision to proceed to the R33 phase is based on finding a statistically significant difference in reduction in PINES activation between the CRD and control conditions. EOT versus baseline contrast maps for all participants in the R33 phase will be entered into a GLM that will use multiple regression to test for differential changes in activation in the regions of interest associated with improvement on clinical outcome variables for distancing training compared to the control condition. The 3 regressors will include: (1) % change in clinical outcome variable; (2) dichotomous treatment type variable; and (3) an interaction term (i.e., product), which identifies activation change related to differential response to the two treatments. The regressors will be centered on zero.

C.7. Power Analyses:

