R61 Phase: The primary outcome measures are decreases from baseline in PINES network activity in the REGULATE (vs. LOOK) conditions in CRD training vs. the CD condition at the 2-, 4-, and 6-week treatment doses. A significant effect at any dose will meet milestone criteria. In our previous work (see C. 1.3.3 above), we obtained a strong effect size of d = 0.73 for 5 days of training. We will, however, power the current study at a more moderate power of d = $\underline{.65}$ to increase our detection sensitivity. We can achieve this at α = 0.05 (\underline{two} — tailed), power = 0.80 with an n = $\underline{39}$ per group (G-Power 3.1). **R33 Phase:** The primary outcome measure for the R33 is the effect of CRD-training upon BPD relevant symptoms, assessed by the Zanarini Rating Scale (see C.4.2.3). A meta-analysis of randomized controlled clinical trials of psychotherapy for BPD reported an effect size of 0.56 for seven stand-alone trials employing BPD-relevant outcomes [65]. Powering to detect an effect size of 0. $\underline{56}$ with a power of 0.80 at \underline{two} -tailed α = 0.05 requires 51 subjects per group.

C.8 Potential Study Complications and Alternative Outcomes

Recruitment Shortfall: We will closely monitor the rate of subject recruitment. If the rate at the 3- or 6-month time points, extrapolated, suggests that the recruitment goals will not be met, we will implement the measures described in section 2.5 (Recruitment and Retention Plan), including, modifying exclusion criteria to allow entry of subjects currently on psychotropic medication and /or in psychotherapy, provided that dose or session frequency has not changed in the prior 2 months. Treatment will be recorded and entered as a covariate in analyses. R61: Alternative Outcomes: It is possible that, contrary to our hypothesis, CRD-, will not be superior to CD-training in reducing PINES activity. While such a finding would not meet milestone criteria, this observation would motivate future research to further explore the active features of CD (as well as nonspecific factors) in the treatment of BPD.

D. Resource Sharing Plan

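### The p<0.01 baseline screen for covariates in the behavioural models recovers almost no precision; adjustment for the baseline outcome should be fixed in advance there and in the R33 Zanarini model

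*Combined protocol and SAP*

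**What the plan says.** C.5.1 (Aim R61-2c) analyses the behavioural ratings with linear mixed models containing training group, session, trial type, their interactions and a random intercept per participant. While noting that the trial is randomised, it adds "variables that are strongly unbalanced at baseline (p< 0.01) as covariates in our models". It does not list the variables to be tested or any covariate that enters regardless of the test. C.5.2 carries the R61 approach into the R33 replication through Aim R33-2.

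For the R33 primary outcome, the Zanarini total score, C.5.2 compares change from baseline to end of treatment by "mixed effect models with group, time and their interaction as fixed effects". It names no covariate and does not restate the screen. Testing is at a common level: "P-values throughout will be 0.05, two tailed".

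The imaging models in C.6.4, including the R61 PINES analysis, have a fixed set: "gender, age, education level, and pre-treatment ALS score will serve as covariates".

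Covariates are mentioned in three other places. Education may be used in the analyses (C.4.1.1), the effect of gender is to be examined for all findings (C.4.2.4), and concurrent treatment is entered if entry criteria are relaxed (C.8).

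**The concern.** Allocation is 1:1 in random blocks (C.4.3.1), so a baseline difference between arms is due to chance. A significance test on that difference says nothing about whether the variable predicts outcome. A strong predictor that happens to be balanced is left out, and an irrelevant variable that happens to be unbalanced is put in. The covariate set cannot be known until the arms have been compared.

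Precision is at stake. The R33 clinical comparison is sized at 80% power with no margin. The most useful covariate, the baseline value of the outcome, is already collected, but the planned group-by-time model does not exploit it fully.

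**Working it through.** **Inputs.** From C.7 and C.4.2.1: the cited meta-analysis "reported an effect size of 0.56 for seven stand-alone trials employing BPD-relevant outcomes"; the calculation is made "with a power of 0.80 at" two-tailed alpha 0.05 and "requires 51 subjects per group"; and "65 BPD subjects will be recruited each for the training and control groups to obtain 51 subjects per group, allowing for 20% loss". The baseline-to-end correlation ρ, the number of variables screened and the R² of any covariate are not in the documents and are assumed below.

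**1. The plan's figure.** By the normal approximation, n = 2(1.960 + 0.842)²/0.56² = 50.06, so 51 per group. The t-test needs 51.03 and has power 0.800 at n = 51. For loss, 51/0.8 = 63.75, so 64, and 52/0.8 = 65, against 65 stated. The plan's figures reproduce.

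**2. How often the screen fires.** The baseline difference needed for p<0.01, in SD units, is t(0.995; 2n−2) × √(2/n):
- n = 51 per group: 2.626 × 0.198 = 0.52 SD.
- n = 39 per group: 2.642 × 0.226 = 0.60 SD.

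Each variable passes with probability 0.01. For k independent variables, the chance that at least one passes is 1 − 0.99^k: 4% for k = 4, 10% for k = 10 and 18% for k = 20.

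**3. What the screen recovers.** The simulation used 20,000 trials per setting, 51 per arm, a single outcome, and ten independent baseline variables of which one is prognostic.

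| R² of prognostic variable | Power, unadjusted | Power, p<0.01 screen |
|---|---|---|
| 0.1 | 0.799 | 0.798 |
| 0.3 | 0.800 | 0.801 |
| 0.5 | 0.800 | 0.801 |

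The prognostic variable was selected in about 1% of trials. With no true effect, the type I error under the screen was 0.047 to 0.049.

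**4. Main-effect covariates and the planned contrast.** The group-by-time term compares within-person changes. A covariate that is constant within a person and enters only as a main effect cancels out of it. In a simulated complete dataset with two visits and a random intercept, the estimate was 0.2812 (SE 0.2047) both with and without the covariate. With 20% of follow-up missing, the SE moved by about 1% or less.

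**5. Where the precision lies.** With two visits, complete data and a free baseline mean in each arm, the group-by-time estimate is the difference in mean change. Taking equal variance σ² at both visits:
- change score: variance 2σ²(1 − ρ);
- adjusted for baseline: variance σ²(1 − ρ²);
- ratio, adjusted to change: (1 + ρ)/2.

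If d = 0.56 is on the change-score scale, the effective size after adjustment is 0.56/√((1 + ρ)/2).

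| ρ (assumed) | Variance ratio | Effective d | Power at 51 per arm | n per arm for 80% power |
|---|---|---|---|---|
| unadjusted | 1 | 0.56 | 0.80 | 52 |
| 0.3 | 0.65 | 0.695 | 0.93 | 34 |
| 0.5 | 0.75 | 0.647 | 0.90 | 39 |
| 0.7 | 0.85 | 0.607 | 0.86 | 44 |

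**The case against.** The strongest reply is that the screen is nearly inert, so the analysis is in effect unadjusted, and an unadjusted analysis of a randomised trial is valid. That stands: the type I error figures show no inflation. Behavioural ratings are also not an R61 milestone (C.2.1), and the PINES analysis that decides progression has fixed covariates.

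A reader might infer more than the documents support:

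- **That the screen is the sole route for covariates.** It is not; C.4.1.1, C.4.2.4 and C.8 give others that do not depend on it. The first two do not specify a model.
- **That the screen governs the Zanarini model.** The sentence sits in the R61 behavioural section, and C.5.2 lists its own terms. Extending the screen there relies on a broad reading of the words 'our models'. What can be said is that no covariate is prespecified for that outcome.
- **That adding the imaging covariates as main effects would raise R33 power.** Step 4 shows that it would not. Gains computed for a single-visit comparison do not describe the planned contrast.
- **That the imaging and behavioural plans contradict each other.** They concern different outcomes and models, so different covariates are not in themselves an error.

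It can also be said that the baseline Zanarini score is already in the mixed model as an outcome. That is true, but with a free baseline mean in each arm the model yields a change-score comparison and gives up the gain in step 5.

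**Conclusion.** The point holds as a loss of precision and of prespecification. The screen selects on chance, makes the behavioural models depend on the data and recovers almost nothing. Separately, the R33 Zanarini model leaves baseline adjustment unused. Its value there is a rise in power from 0.80 to between 0.86 and 0.93 for correlations from 0.7 down to 0.3.

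The variance ratio (1 + ρ)/2 rests on equal variances at the two visits. The power figures rest also on d = 0.56 being on the change-score scale, which C.7 does not state, and on assumed correlations. At ρ = 0.5 the change-score and end-score variances coincide, since 2(1 − 0.5) = 1, so the 0.90 does not depend on the choice of scale. The figures apply to the R33 clinical comparison; the documents allow no similar figure for the behavioural ratings.

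**What to change.** - In C.5.1, delete the p<0.01 rule and report baseline balance descriptively, without tests.
- In the behavioural models and the R33 clinical models of C.5.2, prespecify adjustment for the baseline value of the outcome, either by ANCOVA or by constraining the baseline mean to be equal across arms in the mixed model.
- Optionally add the C.6.4 covariates (gender, age, education level, pre-treatment ALS) with covariate-by-time terms, since main effects alone leave the group-by-time contrast unchanged.

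One limit should be written in. The equal-mean constraint needs a baseline measured before the arms are treated differently. By the order in C.4.3.1, the Zanarini score qualifies. The behavioural ratings come from the baseline scan, which follows randomisation and, by C.2.5, arm-specific instruction for the Regulate trials. For Regulate ratings and reappraisal success the constraint should therefore not be assumed. If ANCOVA is used there, the plan should say that the comparison is conditional on a baseline taken after that instruction.

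The cost is a few sentences in C.5.1 and C.5.2. The variables are already collected, and no participant or visit is added.
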